#### [name]

Use the VAS prior to dosing at the Water Only Evaluation visit and all remaining visits.

The primary endpoint of relief of dry mouth, post dosing, will also be evaluated by using a 5-point ordinal scale where none/(no relief) (1), not enough (2), some/good (3), very good (4), significant/excellent (5) are used.

This will be used after dosing on the Water Only Evaluation visit and Baseline 1 & 2 visits.

## Secondary endpoints

Secondary endpoints will be scored using a 5-point ordinal scale where Poor (1), Fair (2), Good (3), Very Good (4) and Excellent (5) are used. Secondary endpoints are the formulation: feel comfortable in the mouth, effectively lubricates the mouth, soothing to the mouth and effectively moistens the mouth.

Use the 5-point ordinal scale to assess each sample at the Water Only Evaluation and sample evaluation visits after 1 dose at 5-minutes, 30-minutes, 60-minutes, 120-minutes, 240-minutes.

Also used to assess secondary endpoints will be the Visual Analog Scale (VAS) - 10 cm long where the subject will score their mouth dryness. The anchor points of the scale are 0 represents "normal" (ie, no dry mouth symptoms), and 10 representing "the worst imaginable" dry mouth symptoms

It will be used at the Water Only Evaluation and Baseline 1 & 2 visits, after 1 dose at 5-, 30-, 60-, 120-, 240-minutes.

#### Weigh bottles

Weights taken prior to any dosing at Baseline, Period 1 and 2, and after dosing at the End of Treatment for both Period 1 and Period 2 visits.

#### Subject Diary

To record subject's product use, any side effects, and adverse events if applicable.

#### **Product Usability Questionnaires**

This questionnaire will be completed for each sample at End of Treatment Period 1 and End of Treatment Period 2 visits.

## **Product Acceptability Questionnaires**

This questionnaire will be completed for each sample at End of Treatment Period 1 and End of Treatment Period 2 visits.

Page 26 of 36 Status: Release

Version: 3

Issue Date: 07/11/2019 03:08:44 PM CDT

[name]

For description of analysis see section 8.2.1.

## 7. Assessment of Safety

## 7.1 Safety Parameters

The principal measures of safety will be the incidence of adverse events reported during the study.

Only treatment-emergent adverse event will be reported.

Examples of anticipated adverse events are:

- Temporary and mild, mouth or tongue sensations such as:
  - Numbness
  - o Burning sensation
  - o Tingling sensations
  - Taste alteration
- Superficial tissue sloughing on the inner surface of the cheeks, which is transient and painless.

#### 7.2 Adverse Events

The Investigator is responsible for identifying adverse events that occur to each subject throughout the study and follow-up period. An adverse event can occur at any time during the conduct of the study, in any phase of the study or after the study is completed. An adverse event can be identified by the Investigator or reported by the subject.

Note: The Federal Privacy Rule (HIPAA) specifically permits the use and disclosure of protected health information "without written authorization of the individual" when used for public health activities such as reporting adverse events, tracking FDA-related products, enabling recalls, repairs, replacements, lookbacks, or conducting post-market surveillance [45 CFR 164.512]. This use and disclosure is subject to the *minimum necessary* standard, i.e. "the minimum necessary to accomplish the intended use, disclosure, or request" [45 CFR 164.502(b)(1)].

#### **Definitions**

- Adverse event (AE) means any undesirable clinical occurrence in a subject whether or not it is considered to be device or drug related.
- Device-related adverse event (i.e., adverse device effect) is an AE considered by the Investigator to have a reasonable likelihood of being associated with the experimental device.

Page 27 of 36 Status: Release

Version: 3

Issue Date: 07/11/2019 03:08:44 PM CDT

#### [name]

Serious adverse event is an adverse event or suspected adverse reaction which, in the view of either the investigator or sponsor, results in any of the following outcomes: Death, a life-threatening adverse event, inpatient hospitalization or prolongation of existing hospitalization, a persistent or significant incapacity or substantial disruption of the ability to conduct normal life functions, or a congenital anomaly/birth defect. Important medical events that may not result in death, be life-threatening, or require hospitalization may be considered serious when, based upon appropriate medical judgment, they may jeopardize the patient or subject and may require medical or surgical intervention to prevent one of the outcomes listed in this definition.

- Serious adverse device effect is a device effect that has a serious adverse effect on health or safety causing hospitalization or prolonged hospitalization, or is life threatening or causes death.
- Unanticipated adverse device effect is any serious adverse device effect on health or safety or any life-threatening problem or death caused by, or associated with a device if that effect, problem or death was not previously identified in nature, severity or degree of incidence in the investigational plan or application, or any other unanticipated serious problem associated with a device that relates to rights, safety and welfare of subjects.

## 7.3 Recording and Reporting

The Investigator records each material-related adverse event on an Adverse Device Effect Record. Documentation includes the description, severity, seriousness, date of onset and resolution, relationship to the experimental material, action taken and outcome.

The Investigator must promptly report an adverse device effect to the 3M Clinical Research Associate. If the adverse device effect is also considered by the Investigator to be serious and/or unanticipated, the Investigator must report it to the IRB as soon as possible and within IRB requirements.

A serious AE involving a non-3M commercialized product is reported to the 3M study monitor and IRB.

If a subject has no adverse device effect during the study, the absence of such must be recorded on the CRF.

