#### [name]

the subject still meets all the other inclusion/exclusion criteria, the subjects will be randomized into the treatment phase of the study.

Enrolled subjects will be scheduled for 2 additional 5-hour visits and two 60-minute visits. There is also at least a 2-day wash-in period prior to any sample dosing and at least a 2-day wash-out period between 1st and 2nd study periods. Each individual subject will participate in the study for total time of up to 4 weeks. There is the possibility that a subject may develop a study related adverse event during participation. Should this happen, a detailed description of start date and other pertinent information will be recorded on an adverse event form and the subject's continued participation in the study and treatment will be at the Investigator's discretion.

All subjects experiencing an adverse event will be followed until the adverse event is resolved.

Pre-treatment Phase			Treatment Phase				
Screening	(wash-in period)	Water-only Evaluation	Baseline Period 1	End of Treatment Period 1	(wash-out period)	Baseline Period 2	End of treatment Period 2 (End of study)
Start of		-0					(6
wash-in							
(6	68	-1	0	7		9+	16+
	>=2 days				>= 2 days		

Visit

Description/sub-phase Study Day Length of Time

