# 8.2.2 Safety Analyses

All adverse events (AEs) occurring after initiation of study treatment (treatment emergent AEs) will be summarized by severity, relatedness, overall and treatment group. AEs occurring during the screening period will be summarized separately. All AEs will be classified using the MedDRA dictionary.

All verbatim descriptions will be listed for all AEs, along with information regarding onset, duration, severity, relationship to treatment, and action taken.

Serious adverse events will be summarized and presented according to nature, time to onset, duration, relationship to treatment and outcome.

Fisher's Exact tests will be carried out to compare each preferred term between treatment groups. Testing will be carried out at a two-sided alpha level of 0.05.

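### Section 7.3 requires full investigator recording only of material-related adverse events, which does not supply the all-causality, between-product AE analysis planned in section 8.2.2

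*Combined protocol and SAP*

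**What the plan says.** Section 7.3 sets the recording rule: "The Investigator records each material-related adverse event on an Adverse Device Effect Record". The fields are description, severity, seriousness, onset and resolution dates, and "relationship to the experimental material, action taken and outcome". The negative entry is equally narrow: "If a subject has no adverse device effect during the study, the absence of such must be recorded on the CRF". In section 7.2 a device-related event "is an AE considered by the Investigator to have a reasonable likelihood of being associated with the experimental device", whereas an AE as such is defined there without regard to cause.

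For the comparator, section 7.3 has one sentence: "A serious AE involving a non-3M commercialized product is reported to the 3M study monitor and IRB". For the experimental spray, the prompt-reporting duty covers adverse device effects.

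Section 3.5 mentions an adverse event form, introduced by: "There is the possibility that a subject may develop a study related adverse event during participation".

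The analysis in section 8.2.2 is wider: "All adverse events (AEs) occurring after initiation of study treatment (treatment emergent AEs) will be summarized by severity, relatedness, overall and treatment group". It also lists every AE with its relationship and action taken, summarises screening-period AEs separately, and compares each preferred term between treatment groups with Fisher's exact test at a two-sided 0.05 level. Section 7.1, however, says "Only treatment-emergent adverse event will be reported".

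**The concern.** AE incidence is the principal safety measure (section 7.1), clinical safety is a secondary endpoint (section 3.2), and the study is meant to support comparative claims (section 2). The analysis therefore needs each AE on each product, rated in the same way. Section 7.3 applies a causality condition at the point of recording and ties the relationship field to one product. A site could follow it to the letter and still leave gaps in two places: events judged unrelated, and non-serious events on the comparator. For those events, severity, relationship, action and outcome as rated by the investigator are not explicitly required. If recording then differs between products, the difference enters the A-versus-B comparison directly, and ratings that were not made at the time are hard to rebuild later.

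**Working it through.** No figure in the documents depends on this rule, so the main check sets the text side by side. A short calculation then shows what unequal recording could do.

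**Step 1: what section 8.2.2 needs against what the text requires**

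| Needed by 8.2.2 | Explicit requirement elsewhere |
|---|---|
| Every AE, related or not | 7.2: investigator must identify AEs throughout. 7.3: full record only for material-related events |
| Relatedness, for events on A and on B | 7.3: relationship to the experimental material only |
| Severity and action for every AE | 7.3: listed for the Adverse Device Effect Record. No equivalent list for other AEs |
| Non-serious AEs on the comparator | 5.1: diary. Appendix A: AE assessment. 3.5: form for study-related events. No field list in any of them |
| Serious AEs on both products | 7.3: any serious AE involving the comparator is reported. For the experimental spray, only adverse device effects |
| Screening-period AEs, shown separately | 7.1 limits reporting to treatment-emergent events |

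**Step 2: is section 7.3 the only route?** No. Subjects record side effects and AEs in a diary in both periods, whichever product they are using (section 5.1, Visits 3 and 5). The diary is source data and goes to the sponsor for entry (section 3.9). Appendix A schedules AE assessment at Visits 2 to 6 with no relatedness condition, and its footnote mentions adverse event forms at unscheduled visits. These routes show that an event occurred. They do not state that the investigator rates severity, relationship, action and outcome for each one.

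**Step 3: is section 7.3 limited to the experimental spray?** The wording is ambiguous. The term material-related is not defined, and section 3.4 treats all three products as study materials. The relationship field in 7.3 and the device-related definition in 7.2 point to the experimental product only.

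**Step 4: illustration of unequal recording.** Inputs: N = 40 per product (section 8.3). The true per-subject rate p of a given AE term is assumed equal on A and B. Recording on A is assumed complete, and a fraction f of the events on B is assumed recorded. Expected recorded counts are 40p on A and 40pf on B; with p = 0.20 and f = 0.5 these are 8 and 4. The probability of declaring a difference is the sum over x and y of Bin(x; 40, p) × Bin(y; 40, pf), taken over tables whose two-sided Fisher p is at most 0.05. The two products are treated as independent groups, as the planned test implies.

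| p | f = 1 | f = 0.75 | f = 0.5 | f = 0.25 | f = 0 |
|---|---|---|---|---|---|
| 0.10 | 0.017 | 0.021 | 0.043 | 0.094 | 0.206 |
| 0.20 | 0.028 | 0.055 | 0.162 | 0.411 | 0.839 |
| 0.30 | 0.028 | 0.078 | 0.281 | 0.682 | 0.991 |

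With equal recording (f = 1) there is no distortion. With f below 1, the excess appears on A. At a 10% rate the effect is small: a table of 4/40 against 0/40 gives p of about 0.12, and 4/40 against 2/40 about 0.68, so neither reaches 0.05.

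**The case against.** The strongest reply is that section 7.3 governs an additional device-effect record and that AEs in general are collected by the diary, the visit assessments, the investigator's duty to identify AEs and the adverse event form. Much of this stands. A reader might infer that section 7.3 is the only recording rule and that comparator events are therefore lost, for example 4 recorded against 0 where the truth is 4 against 4. The documents do not support that. A reaction to the comparator, which is a study treatment, is naturally study-related, so the section 3.5 form would apply to it.

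A reader might also infer that a serious event on the experimental spray judged unrelated would never reach the sponsor. That too goes beyond the text. Data sheets and diaries go to the sponsor (section 3.9), the monitor reviews CRFs and source documents (section 9), and section 8.2.2 plans a summary of serious events by relationship. What is missing is an express reporting sentence. Nor can bias from unblinded causality judgement be asserted: section 3.3 says that subjects are unblinded and the oral examiner is blinded, but no section says who judges causality.

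The reply does not remove the gap in Step 1. None of the other routes carries a field list or an all-causality rating requirement, and section 7.3, which does carry one, is narrower than the analysis it feeds.

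**Conclusion.** The point holds as an internal inconsistency that should be reconciled. Section 7.3 conflicts with the AE definition in 7.2 and does not supply the ratings that 8.2.2 tabulates, lists and compares. Incomplete or one-sided data is a risk, not an established result. To call the relatedness table meaningless, or the comparison already biased, would go further than the text allows.

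The size cannot be fixed, since the documents give neither AE rates nor recording rates. Under the assumptions in Step 4, halving the recording on B gives a chance of a spurious difference between 0.043 (10% rate) and 0.281 (30% rate), against 0.017 to 0.028 with full recording. Under-recording on B would count against the sponsor's own product. The conflict between 7.1 and 8.2.2 over screening-period events is separate and minor, but it lies in the same text and can be settled in the same amendment.

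**What to change.** - Amend section 7.3 so that every AE, related or not, is recorded on one AE form. It should cover the start of wash-in through the follow-up referred to in section 7.2, on A, B or water.
- Use the same fields throughout: description, onset and resolution dates, period and product in use, severity, seriousness, relationship to the product in use, action taken and outcome. Word the negative CRF entry to cover any AE.
- Keep the Adverse Device Effect Record as an additional form for device-related events.
- Reconcile the serious-AE reporting sentences in 7.3 so that they apply alike to all study products.
- Reconcile section 7.1 with the screening-period summary in section 8.2.2.

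The cost is protocol wording, one form and a little more data entry. AEs are already assessed at each visit from Visit 2 and noted in the diary in both treatment periods.

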#### 8. Statistics

8.1 Data Sets Analyzed

Page 28 of 36 Status: Release

Version: 3

Issue Date: 07/11/2019 03:08:44 PM CDT

#### [name]

The intent-to-treat (ITT) data set will be the primary efficacy data set and will include all subjects randomized in the study. Subjects will be analyzed in the group to which they were randomly assigned. Subjects with missing post-baseline VAS scores will be included in the ITT analysis using appropriate input data sets and multiple imputation method.

A second per-protocol (PP) data set will be defined excluding any subjects with major deviations or lack of compliance with taking their treatments.

The major protocol deviations that will lead to exclusion from the per protocol data set include subjects missing the primary endpoint for one or both treatment periods, subjects not taking product for >= 2 days, and subjects taking excluded dry mouth products.

Deviations not captured above that will result in exclusion from the PP analysis will be defined and justified in a blinded fashion. In addition, documentation will be made of these data classification decisions prior to data lock.

#### 8.2 Statistical Methods

The primary endpoint will be the paired-difference in VAS scores between experimental and active control product after 15 minutes of the first dose on the first day of the treatment period.

#### 8.2.1 Efficacy Analyses

Primary efficacy analysis will be a mixed effects model of the VAS scores with baseline VAS (prior to first dose) included as a covariate and treatment group, period, and order assigned as fixed effects in the model. In addition, subject (group) will be included as a random effect in the cross-over model.

If the upper 95% confidence limit of the difference in VAS scores (experimental-control) is <= 1.5 then non-inferiority of the experimental product relative to the control product will be declared. Simultaneous testing of non-inferiority and superiority will be carried out without inflation of alpha error, maintaining a one-sided 0.025 significance level.

## Secondary efficacy analyses:

To control the type 1 error rate, a fixed sequence of non-inferiority/superiority testing of the VAS dry mouth score differences will be conducted in the following order if the primary analysis at 15-minutes post first dose shows Treatment A is non-inferior/superior to the control Treatment B:

VAS dry mouth efficacy results immediately after use (within 5 minutes)

VAS dry mouth efficacy results 30 minutes after use

VAS dry mouth efficacy results 60 minutes after use

VAS dry mouth efficacy results 120 minutes after use

3M Confidential

Document Name: CLIN-PROT-ICH-US-11-406546 Clinical and Non-Clinical: CLIN-INDEX-3M-SPON-US-11-050038

Page 29 of 36 Status: Release

Version: 3

Issue Date: 07/11/2019 03:08:44 PM CDT

#### [name]

VAS dry mouth efficacy results 240 minutes after use at baseline or at start of treatment period (after first sample dose)

A comparison of Treatment A against water will be carried out using a mixed effects model. The model of the VAS scores will have the baseline VAS (prior to first dose) and treatment group as fixed effects, and subject (group) will be included as a random effect in the model.

The responses on dry mouth relief, lubricating effects, soothing effects, comforting effects, and moistening effect, will be analyzed using a signed rank test for each of the two treatment arms at each time point. P-values will be adjusted using the Holm method for repeat testing done over time (5, 30, 60, 120 and 240 minutes) for families of hypotheses

Area under the curve (AUC) will be computed for the VAS endpoint and will be analyzed using an ANOVA model with baseline values, treatment group, order (or sequence) and period as fixed effects, and subject (group) as the random effect.

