## 2. Study Objectives and Purpose

The purpose of this study is to investigate the efficacy of 3MTM Dry Mouth Moisturizing Spray to reduce symptoms of dry mouth for up to 4 hours and after 7 days of use. In addition, this study aims to support comparative claims.

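### The planned signed rank tests on the five ordinal product ratings state no A versus B contrast and no null, so as written they do not compare the two sprays on those items

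*Combined protocol and SAP*

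**What the plan says.** The sentence at issue is in section 8.2.1, under the secondary efficacy analyses. Its subject is "The responses on dry mouth relief, lubricating effects, soothing effects, comforting effects, and moistening effect", and these "will be analyzed using a signed rank test for each of the two treatment arms at each time point". Multiplicity follows: "P-values will be adjusted using the Holm method for repeat testing done over time (5, 30, 60, 120 and 240 minutes", for families that are not defined further. The sentence names no difference between products, no reference value, and no period or order term.

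Section 6.2 defines the scales. For relief: "The primary endpoint of relief of dry mouth, post dosing, will also be evaluated by using a 5-point ordinal scale", coded 1 (no relief) to 5. Its timing is "This will be used after dosing on the Water Only Evaluation visit and Baseline 1 & 2 visits". For the other four items: "Secondary endpoints will be scored using a 5-point ordinal scale where Poor (1), Fair (2), Good (3), Very Good (4) and Excellent (5", given after one dose at the water visit and the two product visits. The visit steps in section 5.1 (Visits 2, 3 and 5) and the schedule in Appendix A agree that these items are asked only after a dose.

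On purpose, section 2 states: "In addition, this study aims to support comparative claims". Section 3.2 lists comparison of the 3M spray with Biotène and with water among the secondary endpoints.

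**The concern.** A signed rank test needs either paired differences or a stated null for the median. A test done separately for each arm, on a score that has no pre-dose value, has neither. Whatever null the analyst or the software supplies, two per-arm p-values answer whether each product scores above that value. They do not say whether the products differ. Two significant results could be misread as equivalence, and one significant result beside one non-significant result could be misread as a difference.

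Four of these items are named secondary efficacy endpoints. The fifth is the ordinal version of the primary outcome, dry mouth relief. If the contrast is left open, it will be chosen after the data exist. Section 3.3 says subjects cannot be blinded to product, and they provide these ratings themselves, so fixing the contrast in advance is worth doing.

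**Working it through.** **1. The plan's own figure.** Section 8.3 gives a sample size for the VAS primary test only; no power is stated for the ordinal items. The VAS figure reproduces. The noncentrality is (1.5 - 0.5)/1.5 × √33 = 3.83, and at one-sided 0.01 with 32 degrees of freedom the power is 0.910 (0.899 at n = 32). It has no bearing on this point.

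**2. What a within-arm test would have to work on.**

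| Measure | Before dosing | After dosing |
|---|---|---|
| VAS dryness | yes | yes |
| Dry Mouth Inventory | yes (water visit, Baseline Period 2) | no |
| Relief, 1 to 5 | no | yes |
| Four attributes, 1 to 5 | no | yes |

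No change from baseline exists for the five items, and no null is stated.

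**3. What each possible reading delivers.** The simulations assume 5-point scores cut from a normal latent variable, within-subject correlation 0.5 and two-sided 0.05 without Holm. None of these is a document figure.

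- *Per arm, against a supplied null.* With a midpoint of 3 (assumed), n = 33 and 3,000 runs, two identical products are both significant in 0.9%, 61.8% and 100% of runs when their common latent shift is 0, 0.5 and 1 SD. A true latent difference of 0.5 SD between products gives both significant in 35.7% of runs (shifts 0.8 and 0.3) or 76.5% (shifts 1 and 0.5). The pattern follows the common level, not the difference.
- *Each product minus water.* The water-visit scores use the same scales, so this is a proper paired test: a product identical to water is rejected in 5.2% of runs (n = 34). It does not compare A with B.
- *A minus B within subject.* Identical products are rejected in 4.3% to 5.2% of runs, and a 0.5 SD latent difference in about 69% to 70%. Of the three, only this reading addresses A versus B.

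**4. Period effect within the A-B reading.** Write d for the A-B difference and π for the Period 2 minus Period 1 effect. The Period 2 minus Period 1 difference has centre π - d in sequence AB and π + d in sequence BA. Comparing sequences (BA minus AB) removes π and leaves 2d.

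Assumed inputs: 17 per sequence (40 × 0.85 = 34 completers), continuous normal differences, treatment shift 0.6 SD, no Holm.

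| Assumed period shift (SD) | Signed rank on A-B: power | Rank-sum of period differences: power | Signed rank: rejection under no difference |
|---|---|---|---|
| 0 | 0.91 | about 0.90 | 0.049 |
| 0.5 | 0.85 | about 0.90 | 0.029 |
| 1 | 0.67 | about 0.90 | 0.004 |

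Repeat simulations move the power figures by up to about 0.02. On tied 5-point scores with no period effect and a latent shift of 0.5 SD, the rank-sum form has power of about 0.71 against 0.74 for the signed rank test.

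**The case against.** The best reply is that the signed rank test is normally a paired test, that section 8.2 frames the primary endpoint as a paired difference, and that the authors probably meant A minus B. That is plausible, but it is not written. The neighbouring VAS text does name its contrasts, both experimental minus control and Treatment A against water. The disputed sentence also comes directly after the water comparison, so pairing each product with water is another reasonable guess. A sentence open to several different analyses still needs correcting.

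Three stronger readings are tempting, and the documents do not support them.

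- A reader might infer that the secondary endpoints can support no comparison at all. They can: VAS dryness at 5, 30, 60, 120 and 240 minutes is tested A versus B in the fixed sequence, and the AUC model has treatment, order and period terms.
- A reader might infer that the per-arm test is bound to be significant. That holds against a null of zero, where all 33 scores are positive and p = 2 × 0.5^33 = 2.3 × 10^-10. The plan states no such null.
- A reader might infer that leaving out the period effect makes a signed rank test on A-B invalid. With balanced sequences it makes the test conservative, not anti-conservative.

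**Conclusion.** The point holds for the five ordinal items and no further. As written, their analysis has no stated contrast or null and gives no A versus B result. This rests on the text alone and needs no simulation. It should be corrected before the data are analysed, but it does not touch the primary analysis, the VAS fixed sequence or the AUC.

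The simulated figures illustrate the consequence and depend on the assumed score distributions, correlation and shifts. Period adjustment is a preference for efficiency and for consistency with the VAS primary and AUC models. It is not the correction of an error.

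**What to change.** Replace the sentence in section 8.2.1 with wording such as:

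> *At each time point A and B are compared within subject on each ordinal item, by the Wilcoxon rank-sum test of the Period 2 minus Period 1 difference between sequences AB and BA, with the Hodges-Lehmann estimate and 95% CI.*

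Because the between-sequence shift is 2d, report half of that estimate and of its limits as the A-B difference. At a minimum, specify the signed rank test on the paired A-B difference.

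If a comparison with water is also intended, state it as a separate paired contrast. Apply the planned Holm adjustment to the A-B p-values over time within each item, which also defines the families. While the sentence is open, say whether 15 minutes is included: section 5.1 collects these items then, but the Holm list omits it.

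The cost is SAP wording only, with no new data. The rank-sum form gives up a little power on tied scores when there is no period effect (about 0.71 against 0.74 under the assumptions above) in return for holding power when there is one.

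### Section 8.2.1 controls type I error only for the A–B VAS sequence; AUC, A versus water and the five ordinal responses have no gate and no control across them, although the study aims to support comparative claims

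*Combined protocol and SAP*

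**What the plan says.** Section 8.2.1 tests the 15-minute VAS difference for non-inferiority and superiority, "maintaining a one-sided 0.025 significance level". Its secondary part then reads: "To control the type 1 error rate, a fixed sequence of non-inferiority/superiority testing of the VAS dry mouth score differences will be conducted". That sequence opens only "if the primary analysis at 15-minutes post first dose shows Treatment A is non-inferior/superior to the control Treatment B" and runs through 5, 30, 60 and 120 minutes to 240 minutes.

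Three further sets of analyses follow in the same section:

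- **Water.** "A comparison of Treatment A against water will be carried out using a mixed effects model". No time point, level or condition for testing is given.
- **Ordinal responses.** "The responses on dry mouth relief, lubricating effects, soothing effects, comforting effects, and moistening effect" are analysed by signed rank tests at each time. The multiplicity rule is "P-values will be adjusted using the Holm method for repeat testing done over time", with five times listed and a reference to families of hypotheses that are not defined further. No level is stated.
- **AUC.** "Area under the curve (AUC) will be computed for the VAS endpoint and will be analyzed using an ANOVA model". Again there is no level and no condition.

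Section 2 adds: "In addition, this study aims to support comparative claims". Section 3.2 lists the comparison with Biotène and with water among the secondary endpoints. Sections 6.1 and 6.2 name comfort, lubrication, soothing and moistening as secondary endpoints. Section 6.2 treats the ordinal dry mouth relief score as a second form of the primary endpoint, so the five responses are that score plus four attributes.

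**The concern.** The plan says that it controls type I error, but the control stops at the 240-minute VAS step. Everything listed after that step can be tested whether or not the primary succeeds, and nothing shares an error budget across the five responses, AUC and water.

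These analyses are natural material for product claims. AUC summarises the VAS over the four-hour window named in Section 2, and the responses correspond to statements about lubrication, comfort, soothing and moistening. None is labelled exploratory. A favourable chance result on any of them could be presented as a prespecified secondary finding, even after the 15-minute test has failed.

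**Working it through.** **The plan's own figure.** The documents give no overall error rate for the secondary analyses, so there is none to reproduce. The only related figure is the sample size in Section 8.3. A paired t-test with distance to margin 1.5 − 0.5 = 1.0, SD 1.5 and one-sided 0.01 needs n = 33 (power 0.910), as stated. It rests on the primary test alone, so a change to the secondary testing order does not alter it.

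**Inputs.** From 8.2.1: five ordinal responses, five times each under Holm, one AUC test, and A versus water (counted as one test because no time point is given). Assumed: each response is its own family; each family or single test is run at two-sided 0.05; there is no true difference anywhere; the correlation between test statistics is unknown, so a range is shown.

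**Step 1, independence, each family at exactly 5%.**
- Five response families: 1 − 0.95^5 = 0.226 (upper bound 5 × 0.05 = 0.25).
- Adding AUC and one water test: 1 − 0.95^7 = 0.302 (upper bound 7 × 0.05 = 0.35).
- Errors in A's favour only: 1 − 0.975^7 = 0.162, against 0.025 nominal.

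**Step 2, Holm applied over the five times.** With no true difference, Holm rejects something in a family only if the smallest p-value is below 0.05/5 = 0.01. With independent times one family errs at 1 − 0.99^5 = 0.049, five families at 1 − 0.99^25 = 0.222, and all seven at 1 − 0.99^25 × 0.95^2 = 0.298.

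**Step 3, correlation.** The times and responses come from the same subjects, and Holm becomes conservative when its tests are positively correlated. Simulating the 25 response tests, AUC and one water test as standard normal statistics with a common correlation gives:

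| Chance of at least one false positive | Corr. 0 | Corr. 0.5 | Corr. 0.7 |
|---|---|---|---|
| One response family | 4.9% | 4.2% | 3.5% |
| Five response families | 22% | 14% | 9% |
| Plus AUC and one water test | 30% | 19% | 13% |
| Same seven, errors favouring A only | 16% | 9% | 6% |

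At correlation 0.9 the seven-family rate is 7.5%, while the five responses alone fall to about 4%, below the nominal level.

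**Step 4, how the count could grow.** If water were tested at all six VAS times there would be 12 tests or families, giving 1 − 0.95^12 = 0.460 under independence. If the signed rank tests are run within each arm, there would be ten response families instead of five, giving 1 − 0.95^10 = 0.401.

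**The case against.** The strongest reply is that much of the size is assumed. The plan does not say that each response forms its own family or that each is tested at 5%. A reader might infer that 8.2.1 prescribes five separate families at full alpha; the text supports only that the families and their level are undefined. The plural and the phrase about repeat testing over time make separate families the natural reading. If all 25 tests were one family, the responses would be controlled among themselves, but they would still be ungated, and AUC and water would remain uncovered.

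A reader might also treat each response as a single 5% test when allowing for correlation. That gives 18% and 15% for the responses at correlation 0.5 and 0.7, and 23% and 18% with AUC and water. It overstates the problem, because it ignores the correlation between times within each Holm family. The figures above account for it.

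Two further points stand. Section 2 does not say which analyses would support comparative claims, so the use of AUC or a single response for a claim is a possibility, not a stated plan. It is also unclear whether the signed rank test compares A with B or change within each arm; a within-arm test would not support a comparative statement at all.

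Finally, Section 3.2 prespecifies the comparison with water. The lack of a gate does not show that it must become descriptive; a stated place in the hierarchy would also control error.

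**Conclusion.** The gap is real and confined to secondary claims. On any reading, AUC and A versus water have no gate and no level, and the ordinal responses do not depend on the primary result. On the natural reading there is also no control across the five responses.

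Under the assumptions stated, the chance of at least one false positive across the seven families is roughly 13% to 30% for correlations from 0.7 down to 0, against 5% intended. In A's favour alone it is roughly 6% to 16%, against 2.5%. These rates depend on the assumed 5% level, the assumed families and the correlation, none of which the documents give.

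It would be wrong to infer that the main result is compromised: the 15-minute test and its one-sided 0.025 level are untouched. The change is worth making before the data are analysed.

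**What to change.** Amend the secondary part of Section 8.2.1 to say that:

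1. AUC and the ordinal responses are tested for claims only if the 15-minute non-inferiority test succeeds, and AUC has a stated place in the fixed sequence, for example after 240 minutes.
2. The Holm family and its alpha are defined so that error is controlled across responses as well as over time. One pooled family of 25 would do this (first threshold 0.05/25 = 0.002; simulated error about 3.4% at correlation 0.5). So would an ordered list of responses or a split of alpha. The text should also say whether each test compares A with B.
3. A versus water has a stated time point and place in the hierarchy, or is reported with a confidence interval and no test.
4. Results outside this order support no comparative claim.

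The change is to wording only, and the sample size stays the same. The price is lower power for any single ordinal response, and AUC cannot be claimed if an earlier step in the sequence fails.
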